7.1.1 Severity of Adverse Events

The Investigator is to classify the severity of an AE using the DAIDS Toxicity Table provided in [Appendix I](#). If the toxicity table does not provide severity guidelines for certain events, the following definitions will be used:

Table 2: Guidelines for Grading AE Severity

Severity	Characteristic
Mild:	Symptoms causing no or minimal interference with usual social & functional activities
Moderate:	Symptoms causing greater than minimal interference with usual social & functional activities
Severe:	Symptoms causing inability to perform usual social & functional activities
Potentially Life-Threatening	Symptoms causing inability to perform basic self-care functions OR Medical or operative intervention indicated to prevent permanent impairment, persistent disability, or death

It is important to distinguish between serious and severe AEs. Severity is a measure of intensity whereas seriousness is defined by the criteria in **Section 7.2**. An AE of severe intensity need not

necessarily be considered serious. For example, nausea that persists for several hours may be considered severe nausea, but not an SAE. On the other hand, a stroke that results in only a limited degree of disability may be considered a mild stroke but would be an SAE.

If an adverse event changes in severity, the worst severity of the AE should be recorded. Should the AE become serious, the AE record will note an end date and a new entry for the SAE should be recorded with an onset date equal to the date the event met seriousness criteria.

7.1.2 Relationship of AE to Study Drug

The following table should be used as a guideline for assigning the relationship of the adverse event to the study drug.

Table 3: Guidelines for Grading Relationship of AE to Study Drug

Association	Definition
None (not related):	(1) The existence of a clear alternative explanation (e.g., mechanical bleeding at surgical site) or (2) non-plausibility, e.g., the subject is struck by an automobile or cancer developing a few days after drug administration.
Unlikely (remote):	A clinical event, including laboratory test abnormality (if applicable), with an improbable time sequence to drug administration and in which other drugs, chemicals, or underlying disease provide plausible explanations.
Related:	A clinical event, including laboratory test abnormality (if applicable), occurring in a reasonable time relationship to drug administration and which cannot be explained by concurrent disease or other drugs or chemicals. The response to withdrawal of the drug should be clinically plausible.

Adverse events judged as “Unlikely” or “Related” will be defined as “Adverse Drug Reaction”.

7.2 Serious Adverse Events

Information about all serious adverse events (SAEs) must be collected and recorded on the SAE Report form and faxed or emailed to the sponsor within 24 hours of learning of its occurrence.

If follow-up indicates a change in the SAE from serious to fatal or life-threatening, this information needs to be reported within 24 hours. If a non-serious AE becomes serious, this and other relevant follow-up information must also be reported within 24 hours as described above.

(Safety reporting contact information is provided in [Appendix A](#)). The site is to follow their local regulations related to the reporting of SAEs to their local IRB/REB/IEC. An SAE is any undesirable sign, symptom, or medical condition which:

- Is fatal or life-threatening (i.e., an event with an outcome of ‘Death’), or
- Requires or prolongs inpatient hospitalization, or
- Results in persistent or significant disability/incapacity, or
- Constitutes a congenital anomaly or a birth defect; or
- Is medically significant, as determined by a qualified health professional, may jeopardize the subject, and may require medical or surgical intervention to prevent one of the outcomes listed above
- Major Bleeding Events must be reported as SAEs (**See Section 7.1**)
- Any adverse event causing a need for unblinding must be reported as a serious adverse event

Events **not** considered to be SAEs are:

- Hospitalizations for treatment which is elective or pre-planned, for a pre-existing condition that did not worsen; or
- Treatment on an emergency, outpatient basis for an event **not** fulfilling any of the definitions of serious given above and **not** resulting in hospital admission.

All on-study deaths, including new fatal adverse events or adverse events that worsen post-baseline resulting in death, must be reported as the outcome of an associated SAE. If the cause of death is not immediately known the event may be reported initially as “Death”, with the actual diagnostic event term provided as follow-up as soon as it is determined.

Pregnancies are not considered SAEs unless complications result which meet serious criteria. Pregnancy, although not in itself an SAE, must also be reported to the Sponsor within 24 hours of becoming aware on the Pregnancy Report Form, using the contact information provided in [Appendix A](#). Pregnancies will be followed to term in order to determine outcome, including spontaneous or voluntary termination, details of birth, and the presence or absence of any birth defects or congenital abnormalities.

All SAEs which occur after the subject has been authorized for randomization will be reported. SAEs are collected through Day 28 and followed until resolution or final outcome. AEs will be collected after authorization for randomization through Day 28, for those subjects that are randomized.

Any subject with positive anti-ART-123 antibody results will have SAEs/thrombotic events captured beyond Day 28 until antibody results are negative or until the subject's 18 month Follow-Up Visit. Clinical evidence of thrombosis may include deep vein thrombosis (DVT), pulmonary embolism, post-thrombotic syndrome, superficial thrombophlebitis, stroke, and myocardial infarction.

Sites will be informed when subjects are antibody positive, after which SAEs and thrombotic events occurring after Day 28 be collected and reported.

7.3 Expected Adverse Events

Expected Adverse Events are those that are consistent with the current version of the Investigator Brochure, including specificity or severity.

7.4 Expedited Reporting

All serious adverse events meeting the definition of reportable will be forwarded to the proper governing regulatory authority within the mandated timelines set forth by that agency.

Once the safety report has been generated and forwarded to the proper agency, a letter will be written and forwarded to the study Investigators. The Investigators will be instructed to submit this notification to their IRB/REB/IEC as soon as possible according to their local requirements.

7.5 Assessment of Risk Burden

In acknowledgement of the need to provide added oversight for vulnerable populations, monitoring for the degree of burden and risk, and assessment of the appropriateness of continuation of treatment with ART-123/placebo during the dosing period of Days 1-6 will be performed. Since the sepsis subjects enrolled to this study have critically ill conditions at the entry, definitive thresholds based on laboratory assessments or physical examination cannot be defined, and the risk and burden for a subject should be monitored by referring to all the assessments and examinations required for this protocol as well as performed as a standard of care. Additionally, because of the inherent risk of bleeding with compounds such as ART-123, in addition to the assessments called for in the protocol (**Sections 5.6 - 5.10**) study drug must be discontinued in instances where a major bleeding event

(defined in **Section 7.1**) is observed. Additional conditions where study drug must be discontinued are detailed in protocol **Section 2.7.1**.

7.6 Clinical Laboratory Evaluations

For this study, there will be both Local and Central laboratory blood draw requirements. The list below outlines which study specific laboratory blood draws are for central laboratory draws (using the provided central laboratory kit) and which are for local laboratory draws (using hospital stock supplies).

To avoid contamination or clotting, all coagulation tests taken for the purposes of this study should be obtained from an original arterial stick or venipuncture. If it is not possible to obtain blood from an original stick or venipuncture, blood may be collected from an arterial line in which no Heparin is infused. The arterial line will be flushed with NS both prior to and after the blood draw. No coagulation samples can be obtained from a Heparin infused or Heparin coated central line. Heparin must not be used when flushing an arterial line for this purpose. The site staff should use proper collection technique as described in the Central Laboratory Manual. **If an original arterial stick or venipuncture is then used to avoid clotting, the coagulation test tubes should not be the first tube of blood filled. Any other blood tests unable to be obtained from the original arterial stick or venipuncture may be taken from an existing port or line. If a central line is used, exploratory laboratory tests should be the last samples to be collected.**

7.6.1 Central Laboratory Tests:

The following laboratory assessments will be collected and sent to the central laboratory for analysis:

- Serum Chemistry (Na, K, Cl, Bicarbonate, Glucose, Ca, BUN, Creatinine, ALT, AST, Alkaline Phosphatase and Total bilirubin)
- Arterial lactate concentration
- D-dimer
- Anti-drug Antibodies to ART-123
- Plasma thrombomodulin concentration (PK)
- Exploratory Laboratory Tests
 - Coagulation: functional protein C, TAT, F1.2, PAI-1 and ATIII
 - Inflammation: CRP, Microparticles, and C5a

7.6.2 Local Laboratory Tests:

The following laboratory assessments will be collected for analysis at the local laboratory:

- Complete Blood Count with differential (RBC, Hemoglobin, Hematocrit, and WBC with differential count)
- Serum Chemistry (Creatinine, Total bilirubin at Baseline Visit only; albumin and total bilirubin if not performed as SOC and necessary to calculate Child-Pugh in patients with severe liver disease at Screening)
- Pregnancy test; Serum or Urine human chorionic gonadotropin (hCG)
- Platelet count
- Coagulation Panel (Prothrombin time and INR)

7.6.3 Laboratory Sample Categories

There are four types of clinical laboratory evaluations: Safety, Coagulation Panel, Organ Dysfunction, and Exploratory.

Safety laboratory tests include the following:

- Serum Chemistry: Chemistry (Na, K, Cl, Bicarbonate, Glucose, Ca, BUN, Creatinine, ALT, AST, Alkaline Phosphatase, Total bilirubin)
- Complete Blood Count with differential (RBC, Hemoglobin, Hematocrit, and WBC with differential count)
- Pregnancy test: Serum or Urine hCG
- Platelet count
- Antibodies to ART-123.

Note: All subjects that develop positive antibodies to ART-123 at Day 28 will be followed at 3 month intervals until their serum antibody titer level returns back to baseline or for a maximum of 18 months.

Coagulation Panel includes the following tests:

- Prothrombin time

- INR
- D-dimer

Organ Dysfunction labs include the following tests:

- Serum creatinine
- Total bilirubin
- PaO₂/FiO₂ ratio

Exploratory labs include the following tests:

- Coagulation: functional protein C, TAT, F1.2, PAI-1 and ATIII
- Inflammation: CRP, Microparticles, and C5a
- Plasma thrombomodulin concentration (PK)
- Arterial lactate concentration

7.7 Physical Examination

Physical examination is performed at the Baseline Visit. The physical will include general appearance; HEENT; neck; respiratory; cardiovascular; chest; abdomen; lymphatic; musculoskeletal and extremities; skin; and neurologic examination. Routine physical examinations will not be recorded after baseline. Any findings on the baseline physical, that are not attributable to a medical condition present prior to obtaining informed consent and meeting the last inclusion criteria, are to be captured either under a medical diagnosis on the Adverse Event eCRF or as a sign or symptom on the Adverse Event eCRF if not part of an diagnosis. All changes in physical examination from the time the subject met the last inclusion criteria and signed informed consent must be documented and recorded as an adverse event (either under a medical diagnosis or as a sign or symptom if not part of a diagnosis) in the eCRF.

7.7.1 Vital Signs

Vital signs include:

- Blood Pressure
- Respiratory rate
- Heart rate

- Temperature

7.8 Electrocardiogram (ECG)

A 12-lead ECG will be performed as outlined in the “Visit Schedule and Assessments” (beginning with **Section 5**) and the table outlining the “Schedule of Events” (**Section 5.19**). Subject’s ECGs will be read centrally and the final read/interpretation of the ECG will be forwarded to the sites for filing in subject source records and documentation in subject’s eCRF. Clinically significant changes in the ECG findings vs. baseline will be evaluated by the Principal Investigator and recorded as AEs / SAEs as applicable.

8 PROTOCOL AMENDMENTS

8.1 Protocol Amendments

Sponsor retains the responsibility for any protocol amendments. Any change or addition to this protocol requires a written protocol amendment that must be approved by the Regulatory Authorities and the IRB/IEC, as applicable, before implementation.

9 DATA MANAGEMENT

9.1 Documentation

Electronic Case Report Forms (eCRFs) will identify each subject by subject number (compilation of site number and subject number) and subject's initials (per local regulatory guidelines). Originals or copies of all source documents, and correspondence will be kept on file at the investigational site.

The data required by the protocol will be recorded in the appropriate eCRFs. All source data will be available to the study monitor who may perform a 100% data check (comparison of the data recorded in the eCRF with those in the source documents). The source data will also be available for an audit by the Sponsor or the FDA (Food and Drug Administration) and all applicable regulatory agencies at any time.

9.2 Data Collection

In addition to the eCRFs, individual subject files or subject medical records as well as Sponsor approved source data information will be maintained. Data will be entered into eCRFs. The eCRFs will be kept current, so that they reflect the latest observations on the subjects enrolled in the study. The eCRFs will include an audit trail to include changes made, reason for change, date of change, and person making changes.

The original signed informed consent form will be available for review at each study visit. All records will be kept in conformance to applicable national laws and regulations.

Analytical data from the central laboratory will be received in an electronic data file format for incorporation into the study database.

9.3 Database Management

When the subject specific database information has been declared to be complete and accurate the database will be locked. Any changes to the database after that time can only be made with written agreement of the Sponsor.

10 STATISTICAL CONSIDERATIONS

P-values will be reported as 2-sided p-values with the decision criteria discussed in **Section 10.1.1** evaluated using these values. Confidence intervals will be generally reported using traditional 95% two-sided intervals. The primary analysis for this study will be conducted on the data up through Day 28. Long-term survival status data will be analyzed once it becomes available following the analysis of the data through Day 28.

Randomization will utilize permuted blocks with a 1 to 1 ratio and will be stratified by site.

10.1 Sample Size and Power Considerations

The primary analysis for this study will be based on a stratified Cochran-Mantel-Haenszel test. For sample size and power calculations an unstratified Cochran-Mantel-Haenszel (chi-squared) test has been used. A sample size of 800 subjects provides 80% power if the following assumptions are made:

1. 5% two-sided α level

2. 8% treatment effect (24% placebo mortality rate vs. 16% ART-123 mortality rate)
3. 1 to 1 randomization

The assumed treatment effect and mortality rates are based upon post-hoc results from study 2-001 and assume the Day 28 mortality status will be known for all subjects.

If the true treatment effect is 12% (24% vs. 12%) a sample size of 800 provides greater than 80% power when a 0.1% alpha level is used.

These sample size and power calculations were performed with Pass 2007.

10.1.1 Decision Guidelines

The primary analysis of this Phase 3 trial is formally based on a two-category decision guideline. To be specific, the decision guideline for this trial is based on whether the observed two-sided p-value associated with comparison of the 28-day survival for the ART-123 arm vs. the placebo arm is, between 0.05 and 0.001 or less than 0.001.

1. If the two-sided p-value is between 5% and 0.1% then the ART-123-based regimen will have met the generally accepted level of evidence (false positive error rate) required to demonstrate efficacy.
2. If the two-sided p-value is less than 0.1% and supporting analyses corroborate this finding ART-123-based regimen will have provided highly reliable and statistically strong mortality results in a disease with limited treatment options. A second confirmatory study would then not be required.

In this 800 subject study an observed treatment benefit of approximately 6% is expected to result in a two-sided p-value less than 5% and a difference of approximately 9% is expected to result in a two-sided p-value less than 0.1%. A sample size of 800 subjects and these assumptions also provide 32% power for a 0.1% two-sided α level.

10.2 Analysis Populations

The primary efficacy analysis population will be the Full Analysis Set, FAS. The Full Analysis Set will consist of all randomized subjects who receive study drug and will be used for efficacy analyses. The Safety population will consist of all subjects who receive drug and will be used for safety analyses.

10.3 Study Stopping Rules / Interim Analyses

The Data Monitoring Committee (DMC) will use the following stopping rules regarding stopping the study early for safety, efficacy or futility.

10.3.1 Stopping for Safety

Termination or modification of the study due to safety concerns will not be limited to a fixed set of analyses. The DMC will be provided with unblinded safety data, including unblinded SAE reports, prior to scheduled data review meetings or upon request.

10.3.2 Stopping for Efficacy

Early termination of the study for efficacy will not be actively pursued unless it would be unethical to continue the study based upon the magnitude of benefit observed. In this situation should the primary efficacy results surpass an O'Brien-Fleming type boundary with Lan-DeMets implementation based upon a two-sided alpha level of 0.001 and the DMC believes the study results are extremely robust and so positive it is unethical to continue the study they may recommend termination for efficacy.

10.3.3 Stopping Due to Lack of Clinically Meaningful Benefit/Futility

An analysis to rule out clinically meaningful benefit will also be performed. The goal of these analyses is to stop the study if sufficient evidence exists that there is not a clinically meaningful treatment benefit. The futility analyses will be conducted with the use of a lower O'Brien-Fleming type boundary. This boundary will be constructed using a one-sided alpha level of 0.20 and the hypothesis: the 28-day mortality rate on ART-123 is reduced by 6%. Should interim analyses be performed after the 600 subjects time-point (75% information) the DMC will interpret the results of the futility calculations in context of the remaining enrollment.

10.4 Handling of Missing Data

Missing data will not be imputed for summarization; summary statistics will be reported based upon observed data.

Exception: for testing of the primary endpoint, Day 28 mortality status, subjects with unknown mortality status will be imputed. Investigators will be asked to assess if at the last point they had

contact with the subject, the subject's health was such that it was unlikely they would be alive at Day 28. If so, it will be assumed the subject was dead at Day 28 otherwise they will be classified as alive for the primary analysis.

10.5 Efficacy Analysis

10.5.1 Primary Analysis

The primary analysis will test the difference in the 28-day all-cause mortality rates between treatment groups in the Full Analysis Set. This analysis will be based upon a Cochran-Mantel-Haenszel test controlling for the randomization strata, site. Sites with low enrollment will be pooled. Subjects with missing mortality status at Day 28 will have their mortality status imputed as outlined in **Section 10.4**. To investigate the degree of variance reduction resulting from the stratification an unstratified test (chi-squared test) of the primary endpoint will be conducted.

Summary measures of survival status at the end of treatment and Day 14 will also be produced.

10.5.2 Secondary Analyses

Descriptive statistics will be used to summarize secondary endpoints. The difference in alive and event free days will be tested using a stratified Wilcoxon test (van Elteren test). Survival time will be summarized using Kaplan Meier methods and tested with a stratified log rank test.

10.6 Safety Analysis

10.6.1 Extent of Exposure

Duration of treatment and amount of drug received will be summarized.

10.6.2 Concomitant Medications

Concomitant medications will be coded by the World Health Organization (WHO) Drug Dictionary and tabulated by treatment group. Medication taken prior to treatment will be summarized separately.

10.6.3 Adverse Events

The incidence of adverse events (AEs), treatment-related AEs, AEs leading to discontinuation, serious adverse events (SAEs), fatal adverse events and AEs by severity will be tabulated by treatment received. These AEs will be classified by system organ class and preferred term using the Medical Dictionary for Regulatory Activities (MedDRA). For incidence reporting, if a subject reported more than one AE that was coded to the same system organ class or preferred term, the subject will be counted only once for that specific system organ class or preferred term. Once the patient is authorized to randomize, SAEs will be collected through Day 28. Once randomization has occurred both AEs and SAEs are collected.

10.6.4 Major Bleeding Events

The number of subjects with major bleeds, as defined in [Appendix B](#), will be compared between treatment arms, as will the numbers of subjects with serious major bleeding events. The number of major bleeding events will be compared between groups at Days 3, 7, 14 and overall.

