2.3 Rationale for Study Design

ART-123 treated subjects with infection and coagulopathy have shown reduced mortality in a Phase III clinical trial conducted in Japan and a positive trend of reduced mortality in a Phase IIb clinical trial conducted globally. These earlier studies used various criteria for DIC to identify subjects with coagulopathy. This DIC based approach was not fully successful in selecting subjects most likely to respond to ART-123, perhaps because of changes in the methods of identifying subjects with DIC. These studies did not require organ dysfunction other than DIC. Analysis of data from the global Phase IIb trial showed that subjects with cardiac or respiratory organ dysfunctions and coagulopathy at study entry had better response to treatment than subjects without these conditions and it was not always feasible to identify the cause of renal or hepatic dysfunction as sepsis or “other”.

The population for the present study will be limited to subjects with cardiovascular and/or respiratory dysfunction, plus coagulopathy in addition to infection characterized by a known site of the infection, fever/hypothermia and the typical WBC response to infection (leukocytosis, leukopenia, or left shifted differential count).

For clarity, both cardiovascular and respiratory dysfunction have been defined using well-established criteria, including vasopressor requirement after fluid resuscitation for cardiovascular dysfunction, and mechanical ventilation requiring intubation for hypoxemia ($\text{PaO}_2/\text{FiO}_2 < 250$ or $\text{PaO}_2/\text{FiO}_2 < 200$ for subjects with a lung infection) for respiratory dysfunction.

Women of child-bearing potential will be allowed into the study if they have a negative pregnancy test (serum or urine hCG) obtained during the current admission to the hospital. The active drug ART-123 has a half-life of approximately 20 hours. Study drug is administered for up to 6 days to subjects who are either in shock and/or on a ventilator. Ten half-lives will have passed 8 days after the last dose; therefore, there is no reasonable likelihood that such study subjects will become pregnant during the period that drug is present in the patient.

The dose and duration of treatment have been established in preclinical and clinical trials.

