#### **4.4.6 Bleeding Events**

A summary table for the number and percent of unique subjects with at least one major bleeding event during the 28 day study period, along with 95% exact confidence interval of the bleeding rate for each treatment and the exact risk difference between two treatment groups in bleeding rates, will be presented using the safety population. The count and percent of unique subjects experiencing at least one bleeding event by Study Days 3, 7, and 14 will be presented in the same table, but confidence intervals and risk difference will not be provided. Subjects will be counted as having experienced a major bleeding event from the earliest recorded event through all subsequent time points.

A bleeding event is considered on-treatment provided it occurs within five days past last dose. An after-treatment event is any event with an onset date of six or more days past last dose date. A summary of on-treatment and after-treatment major bleeding events will be presented by treatment arm and overall. If a subject experiences both an on-treatment and after-treatment event the subject will be counted in both summaries; that is, on-treatment and after-treatment event summaries may not be disjointed.

A similar summary will be presented for serious major bleeding events as well.

Additionally, the differences in major bleeding event rates will be presented by country, new infections, concomitant heparin use through day 7, renal function through day 7, baseline RRT, and on treatment RRT

Adverse events and serious adverse events identified as bleeding events will be summarized by primary system organ class (SOC) and preferred term (PT) for on treatment and off treatment separately.

All bleeding event data will be presented in a data listing.

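### The protocol promises a between-group comparison of major bleeding at Days 3, 7 and 14, but the SAP specifies a risk difference and interval for the whole population only over 28 days

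*Protocol*

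**What the plan says.** Protocol 10.6.4 makes two commitments. The numbers of subjects with major bleeds "will be compared between treatment arms, as will the numbers of subjects with serious major bleeding events". It then adds a timed comparison: "The number of major bleeding events will be compared between groups at Days 3, 7, 14 and overall". It names no statistic for either.

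SAP 4.4.6 carries this out in one table on the safety population. For the 28-day period it gives the number and percent of subjects with a major bleed, "along with 95% exact confidence interval of the bleeding rate for each treatment and the exact risk difference between two treatment groups in bleeding rates". For the earlier days it says: "The count and percent of unique subjects experiencing at least one bleeding event by Study Days 3, 7, and 14 will be presented", and then "but confidence intervals and risk difference will not be provided".

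The same section plans a summary by arm of on-treatment and after-treatment major bleeding, with no risk difference or interval specified for it. The window is defined thus: "A bleeding event is considered on-treatment provided it occurs within five days past last dose". SAP 3.7 rules out testing of safety endpoints and points to 4.4.6 for the bleeding intervals.

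On exposure, treatment lasts six consecutive days (Protocol 2.1), and Protocol 2.3 says: "The active drug ART-123 has a half-life of approximately 20 hours".

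**The concern.** Major bleeding is a primary safety endpoint, and Protocol 7.5 acknowledges that bleeding is an inherent risk of compounds such as this one. The days at which the SAP withholds the effect estimate are the days that span exposure. The one whole-population contrast that comes with an interval runs well past it.

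Two things are at stake. First, the SAP departs from a stated protocol comparison without giving a reason. Second, if major bleeds unrelated to the drug occur in both arms after exposure ends, they add variance to the 28-day contrast. A drug-related excess would then be reported with a wider interval than the same data would give for the treatment period.

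The wording adds two smaller mismatches. The protocol's timed comparison counts events, while the SAP counts unique subjects. And the SAP sentence on Days 3, 7 and 14 drops the word major, so one table could be read as mixing two definitions.

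**Working it through.** **Setting the texts side by side**

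| Time point | Protocol 10.6.4 | SAP 4.4.6 |
|---|---|---|
| Days 3, 7, 14 | events compared between groups | count and percent of subjects; risk difference and interval withheld |
| On treatment (to five days past last dose) | not mentioned | summary by arm; no risk difference or interval specified |
| Overall / 28 days | events, and subjects with major bleeds, compared | exact intervals and exact risk difference |

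**Exposure within the 28 days.** With the sixth dose on Day 6, the SAP's on-treatment window closes at about Day 6 + 5 = Day 11, leaving 28 − 11 = 17 days after treatment. Ten half-lives are 10 × 20 = 200 hours, or about 8 days, which is how Protocol 2.3 counts it; this reaches about Day 14.

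**Sample size.** The documents give no bleeding rate and no power statement for bleeding, so the only figure to reproduce is the one for mortality. It confirms the use of n = 400 per arm. Power = Φ{[|p1 − p0| − 1.96·√(2p̄(1 − p̄)/n)] / √[(p1q1 + p0q0)/n]}. With 24% versus 16%, p̄ = 0.20: (0.08 − 1.96 × 0.02828)/0.02814 = 0.873, so power is 80.9% against the stated 80%. At the 0.1% level the same formula gives 32.1% against the stated 32%.

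**Illustration for bleeding (all rates assumed).** Take 4% on ART-123 versus 2% on placebo in the treatment period, and add the same later background to each arm. Half-width = 1.96·√[(p1q1 + p0q0)/400].

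- Treatment period: 1.96·√[(0.04 × 0.96 + 0.02 × 0.98)/400] = 1.96 × 0.0120 = 2.4 points.
- Day 28 with 3% background: 1.96·√[(0.07 × 0.93 + 0.05 × 0.95)/400] = 1.96 × 0.0168 = 3.3 points.

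| Later background | Rates compared | Risk difference | 95% half-width | Chance interval excludes zero |
|---|---|---|---|---|
| none | 4% vs 2% | 2.0 points | 2.4 points | 38% |
| 1% | 5% vs 3% | 2.0 | 2.7 | 30% |
| 2% | 6% vs 4% | 2.0 | 3.0 | 25% |
| 3% | 7% vs 5% | 2.0 | 3.3 | 22% |
| 5% | 9% vs 7% | 2.0 | 3.8 | 18% |

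The last column uses the power formula above and is only a reading aid, since the SAP plans no safety test. The half-widths are large-sample (Wald) values; the SAP's exact intervals would differ somewhat.

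**Is the risk difference itself diluted?** If later bleeds count only in subjects without an early one, each Day 28 risk is p + (1 − p)b, and the difference becomes (p1 − p0)(1 − b). With b from 1% to 6% it shrinks by 1% to 6% of its value; at b = 3% it goes from 2.00 to 1.94 points. The loss is in precision, hardly in the estimate.

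**The case against.** The strongest reply is that the SAP does let the reader compare the arms early. Counts and percents at Days 3, 7 and 14 stand in the same table as the 28-day row. Major bleeding is also summarised by arm on and after treatment, serious major bleeding similarly, and bleeding adverse events separately on and off treatment. The protocol says only that groups will be compared, so side-by-side percentages can be called a descriptive comparison, and anyone can derive an interval from the counts of subjects. The DMC reviews unblinded safety data throughout (Protocol 10.3.1). SAP 4.1 requires departures from the protocol's analyses to be explained in the study report. All of this stands, and it makes this a question of final reporting rather than of subject protection. It does not explain why the SAP uses the risk difference to compare major bleeding over 28 days and then refuses it at three of the four time points the protocol names.

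A reader might infer that bleeding is compared only at Day 28. The planned early and on-treatment summaries contradict that. The 28-day row is not even the only planned difference, because 4.4.6 also presents differences in major bleeding rates by country and several other factors.

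A reader might also infer that the 28-day window dilutes any early excess, or that deaths help to hide one. The risk difference is almost unchanged, as shown above. If deaths followed the design assumption of 24% on placebo and 16% on ART-123, placebo subjects would have less time at risk, which would tend to enlarge a 28-day excess on ART-123. The sound form of the point about deaths is that the longer window is more exposed to unequal follow-up, whichever way that runs.

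Finally, the earliest rows are not better by construction. Day 3 covers only three of six doses, and Day 7 misses the tail of exposure. The on-treatment row matches exposure most closely.

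**Conclusion.** The concern holds as a mismatch on a primary safety endpoint: the protocol commits to comparing major bleeding at Days 3, 7 and 14, and the SAP expressly withholds at those days the effect estimate it uses for 28 days. The consequence is some loss of precision for drug-related bleeding, in proportion to how much background bleeding occurs after exposure.

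Under the assumed 4% versus 2% with 400 per arm, the half-width grows from 2.4 points to between 2.7 and 3.8 points for 1% to 5% later background, and not at all if there is none. Every one of those bleeding rates is an assumption, so the direction is firm but the size is not. The protocol names no statistic, so it cannot be said that it promised a risk difference or an interval. This is an inexpensive improvement to make, not a threat to the trial's conclusions.

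**What to change.** In SAP 4.4.6:

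- Delete "but confidence intervals and risk difference will not be provided".
- Report the exact risk difference and its 95% confidence interval for major bleeding by Study Days 3, 7 and 14 and for the on-treatment window (through five days past last dose), beside the 28-day row, labelled descriptive.
- In the sentence on Days 3, 7 and 14, change bleeding event to major bleeding event.
- Reconcile the unit of count: either add the number of major bleeding events by arm at each time point, as the protocol has it, or state and justify the use of unique subjects.

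The cost is a few extra rows in an existing table. It needs no new data and no change to the sample size or to alpha. The one drawback is a few more descriptive intervals without multiplicity control, which the label should make plain.
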